4 STUDY DESIGN

4.1 Overall Design

This is natural history study (comparison of vaping to non-vaping adolescents) and an open label pilot study (MBSR intervention to vaping adolescents).

This single-sight study will be carried out at the NIDA-IRP's Biomedical Research Center in Baltimore, MD.

The study will enroll up to 60 nicotine vaping youth and 60 non-vaping youth to obtain complete data on N=40 tobacco vaping youth 13-18 years old and N=40 age, sex, race/ethnicity, SES matched typically developing (TD) non-vaping/non-smoking youth. The study intervention, given to vaping teens, is a Mindfulness-Based Stress Reduction (MBSR) training. The intervention is a group-based instructor-led mindfulness-based stress reduction (MBSR) training.

Abbreviated Title: Mindfulness and Teen Vaping

Version Date: 07/21/2025

NIH IRB#: IRB001855

The MBSR intervention will consist of eight weekly 2-hour sessions and one 3-hour retreat that will take place at the NIDA BRC. Each group will consist of 8-12 participants.

Participants will be recruited online and via our concurrent vaping survey study. Only nicotine vaping youth will participate in the MBSR intervention. The vaping group will participate in one to four primary data gathering visits, all but one of which can be done virtually. The visit that will include the first MRI scan visit must take place in-person 0-3 months pre-MBSR intervention, and the second MRI scan visit will take place 0-6 weeks post-MBSR intervention. The TD non-vaping group will not participate in the MBSR intervention, and therefore will only participate in the baseline assessments (one to four virtual or in-person visits including the first in-person MRI scan). For those receiving the MBSR intervention, there will also be four monthly follow-up visits which may be administered in-person or virtually. The one at the conclusion of MBSR training may be combined with scan 2. The MBSR visits are optional, and as long as one visit is completed, the other visits if missed will not result in a deviation.

We hypothesize that teens who vape will differ from those who do not on all behavioral, cognitive and imaging measures and that the MBSR intervention will alter these measures in the vaping teens so that they will differ less from their non-vaping counterparts.

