4.4 End-Of-Study Definition

A frequent nicotine vaping participant is considered to have completed the study if they have completed the baseline assessment, all 9 weeks of the MBSR intervention, the pre- and post-intervention MRI scans, and the follow-up assessments. There will be an end of intervention assessment and three follow-up assessments (once per month for three months and may be conducted virtually) after the last MRI scan. The final follow-up marks the end of the study for the participant.

A non-vaping participant is considered to have completed the study if they have completed the baseline assessment and one MRI scan.

(SoA), **Section Error! Reference source not found..**

Abbreviated Title: Mindfulness and Teen Vaping

Version Date: 07/21/2025

NIH IRB#: IRB001855

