6 STUDY INTERVENTION

6.1 Study Interventions(s) or Experimental Manipulations(s) Administration

6.2 Study Intervention or Experimental Manipulation Description

Description of intervention: MBSR Program: The adapted MBSR program is a structured evidence-based 9-week program that consists of eight weekly 2-hour sessions and one 3-hour retreat. We will conduct 4-6 MBSR groups of 8-12 participants each. The program content includes: 1) material related to mindfulness, meditation, yoga, and the mind-body connection; 2) experiential practice of mindful meditation (sitting, lying down, walking, etc.), mindful yoga, and “body scan”, and encouragement of home practice; and 3) group discussion of barriers to effective practice. MBSR group discussions are focused on issues related to the practice of mindfulness in daily life. As with our previous studies, the group will be led by an instructor trained in MBSR, experienced with mindfulness instruction in youth with psychiatric conditions, using the adapted MBSR workbook. MBSR program fidelity will be tracked using a previously developed checklist consisting of the main concepts, content, activities, and qualitative assessment for each class.

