7.1 Discontinuation of Study Intervention/Experimental Manipulation

Participants who engage at any level in the MBSR training and are not disruptive will be allowed to continue with the intervention and the protocol in general. Only those who express a desire to withdraw from the MBSR, persist in disruptive behaviors during sessions, or are lost to follow-up will be discharged from the study. There are no safety endpoints that need follow-up after discontinuation of MBSR or the study.

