9.3 Populations for Analyses

- Modified Intention-to-Treat Analysis Dataset: All frequent nicotine vaping participants approved to participate in the MBSR intervention who complete the first scan day will be included in the comparison of vaping to non-vaping teens. Non-vaping teens who complete the scan will be included in this analysis.
Frequent nicotine vaping participants who completed the study intervention (regardless of number of sessions actually attended) and complete both MRI scans will be included in the pre-post imaging comparison in the vaping group. If they also complete at least one follow-up visit, they will be included in the assessment of effect of MBSR on vaping and related outcome measures.

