9.4.3 Analysis of the Secondary Endpoint(s)

Our secondary endpoint aims to determine the feasibility and acceptability of the MBSR intervention and thus we will collect descriptive data to determine the feasibility and acceptability via program engagement. To assess program engagement: the # of MBSR group sessions attended will be calculated for each participant and the # and proportion of participants completing 50%, 75%, and 100% of group sessions will be calculated.

To assess preliminary efficacy, we will use the data as described for Primary Endpoint 2. Primary and secondary outcomes for the clinical trial are shown below.

| Outcome Type | Measures Used for Outcome | Definition of Outcome |
|--|---|--|
| Primary Efficacy Outcomes | TLFB, Urine Cotinine Test | The primary outcome measure is change in vaping frequency at the post-MBSR follow-up MRI session. |
| Primary Group Effect Outcome | FFMQ mindfulness scale, Difficulties in emotion regulation scale (DERS), General Substance Use History Questionnaire, Digit Span assessment | The primary outcome measure for the vaping vs TD group comparison will be the substance use, mental health and cognitive function measures at baseline. |
| Secondary Efficacy Outcomes | TLFB, FFMQ mindfulness scale, Difficulties in emotion regulation scale (DERS), Digit Span assessment | Secondary efficacy outcomes are changes in craving, mindfulness, negative emotions (depression, anxiety), emotion regulation and cognitive measures from baseline to post-MBSR study visit. |
| Primary Feasibility/Acceptability Outcomes | Recruitment, retention, program engagement, app use data | MT intervention will be considered acceptable and feasible for use in this population if at least 75% of participants are retained through the EOT, and at least 75% of participants download the C2Q app and complete 1 module. |
| Secondary Feasibility/Acceptability Outcomes | Participant self-report on MBSR program and CTQ utility, ease of use, etc. | Secondary outcomes for feasibility/acceptability are self-report responses about the helpfulness and utility of the MBSR program and C2Q app. |

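### The vaping-outcome set requires both MRI scans and has no missing-data method, so vaping change and abstinence may be overstated; the 75% retention rule lacks a denominator and an attendance term.

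*Combined protocol and SAP*

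**What the plan says.** Section 9.3 puts three sets under one label:

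- Baseline comparison: approved vapers "who complete the first scan day will be included in the comparison of vaping to non-vaping teens". Nothing after scan 1 is required.
- Pre-post imaging: "Frequent nicotine vaping participants who completed the study intervention (regardless of number of sessions actually attended) and complete both MRI scans will be included".
- Vaping and related outcomes: "If they also complete at least one follow-up visit, they will be included in the assessment of effect of MBSR on vaping".

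Section 9.4.1 tests change in continuous measures with paired t-tests. No section says how missing outcomes are handled. Section 7.1 states: "Only those who express a desire to withdraw from the MBSR, persist in disruptive behaviors during sessions, or are lost to follow-up will be discharged". Section 4.1 plans to "enroll up to 60 nicotine vaping youth and 60 non-vaping youth to obtain complete data on N=40 tobacco vaping youth" and makes sessions after the first optional.

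On timing, the Follow-up Assessments text in Section 8.2 lets substance-use and other measures be taken in person or by video within three weeks of MBSR. Scan 2 may come at about six weeks, and the monthly visits are dated from the first assessment rather than from the scan. Table 1 lists the Timeline Follow-back (TLFB) at Visit 1 and Visits 12-15, not at scan Visit 11, which may or may not be combined with Visit 12 or 13. Sections 9.4.3 and 9.4.5 instead place the primary vaping outcome and the second TLFB at the post-MBSR MRI visit.

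The feasibility rule in Section 9.4.3 requires that "at least 75% of participants are retained through the EOT" and that the same share download the app and finish one module. The section also tabulates, without a pass mark, the shares reaching 50%, 75% and 100% of sessions. Section 4.4 counts a vaper as having completed the study only after, among other things, "all 9 weeks of the MBSR intervention".

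**The concern.** The word *also* in the third definition makes the vaping-outcome set a subset of the two-scan set. A teen who starts MBSR and gives TLFB data at all four follow-up visits, but misses scan 2, is removed from the vaping analysis although the outcome was observed. That is a selection on post-baseline behaviour, which the intention-to-treat name is meant to exclude.

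The loss need not be random. Teens who ask to leave MBSR are discharged, and the plan does not say whether their outcomes are still collected. Scan visits are rescheduled after a positive drug test with signs of intoxication (Sections 5.6 and 8.2), so a missing scan 2 may itself be related to substance use. A paired t-test on the remaining pairs has no protection against this.

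The feasibility rule has a parallel weakness. Without a denominator, retention can be computed on different groups of teens, and without an attendance term it can be met by teens who came once. Section 2.2 says that the pilot's feasibility, acceptability and preliminary efficacy results will inform later controlled trials, so an optimistic figure here would carry forward.

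**Working it through.** **1. The plan's own figures.** The sample sizes in Section 9.2 reproduce. With a two-sided one-sample t-test, 100 time points assumed, and SD = √(0.5² + 0.75²/100) = 0.506, N is 11, 21 and 12 against the stated 11, about 21 and 11. They do not enter this point. The figures that do are the enrolment ceiling and the complete-data target in Section 4.1: 40/60 = 66.7%. No dropout rate, effect size or abstinence rate is given, so everything below is a range under stated assumptions.

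**2. Who is in which set (from the text).**

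| Vaper | Baseline comparison | Pre-post imaging | Vaping outcomes |
|---|---|---|---|
| Scan 1, MBSR, scan 2, at least one follow-up | in | in | in |
| Scan 1, MBSR, four follow-ups, no scan 2 | in | out | **out** |
| Scan 1, withdraws from MBSR, discharged | in | out | out |

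The second row is the fault: the outcome exists and is discarded.

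**3. Dilution if non-completers do not change.** With retention r, all-starter mean = r × completer mean + (1 − r) × 0, so completer mean ÷ all-starter mean = 1/r:

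- r = 0.90: 1.11
- r = 0.75: 1.33
- r = 40/60: 1.50
- no loss: 1.00

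**4. Selection related to benefit.** Assume a normal model in which completion correlates ρ with benefit. The completer mean is then too favourable by ρ × φ(z)/r standard deviations of change, where z cuts off the proportion r. φ(z)/r is 0.545 at r = 66.7%, 0.424 at 75% and 0.195 at 90%.

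| ρ | r = 66.7% | r = 75% | r = 90% |
|---|---|---|---|
| 0 | 0 | 0 | 0 |
| 0.2 | 0.11 | 0.08 | 0.04 |
| 0.4 | 0.22 | 0.17 | 0.08 |
| 0.6 | 0.33 | 0.25 | 0.12 |

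A negative ρ reverses the sign.

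**5. Abstinence (hypothetical 10 abstainers among 40 completers).** 10/40 = 25.0%. With missing counted as vaping it is 10/45 = 22.2% for 5 lost, 10/50 = 20.0% for 10 lost, and 10/60 = 16.7% for 20 lost. Exact 95% intervals are 12.7-41.2% for 10/40 and 8.3-28.5% for 10/60.

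**6. Feasibility rule.** Attending one of nine sessions is 11.1% attendance. Such a teen can still be retained through end of treatment and finish one app module, so the rule can pass with every teen at that level. On a denominator of 60 the retention bar is 0.75 × 60 = 45; on 40 it is 30. The same count can pass or fail according to which is meant.

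**7. Group clustering.** Section 6.2 says "We will conduct 4-6 MBSR groups of 8-12 participants each". The intraclass correlation (ICC) is not in the documents. Simulating the one-sample t-test on change scores with 4 groups of 10 or 5 groups of 8 gives a type I error of about 6% at an assumed ICC of 0.01 and 9-10% at 0.05.

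**The case against.** Much of the other side stands.

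- The label is not wrong throughout: the baseline comparison uses everyone with scan 1, and a paired imaging comparison cannot avoid needing two scans.
- Sections 9.4.3 and 9.4.5 tie the primary vaping outcome to the MRI visit, and its measures include urine cotinine, which a video call cannot supply. The two-scan condition may therefore be deliberate. This stands only in part. Table 1 and Section 8.2.1 place cotinine at Visits 12-15 as well, self-reported TLFB needs no scan, and Table 1 omits TLFB at Visit 11. It shows a conflict to settle rather than a reason to discard follow-up data.
- Low attenders stay in the study and are analysed whatever number of sessions they attended. That is sound and would tend to dilute an effect.
- A reader might infer from 40 of 60 that retention is expected to miss the 75% bar. The documents do not support this. Forty is a target for complete data, not for retention to end of treatment, and 60 is a ceiling that may include screen failures.
- A reader might say that attendance is ignored, or that Section 4.1 defines completion as one session. Attendance is reported descriptively, and Section 4.1 says only when missed sessions are not deviations. The real mismatch on *completed* is Section 4.4 against Section 9.3.
- Section 3 places vaping change and app engagement under secondary objectives, in an uncontrolled pilot. That lowers the weight, although the table in Section 9.4.3 calls vaping change a primary efficacy outcome.

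**Conclusion.** The text itself establishes that the vaping-outcome set drops teens whose vaping was observed, that no missing-data method is given, and that the retention rule has neither a denominator nor an attendance term. These are faults in stated rules, not missing detail.

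A reader might go further and conclude that efficacy and acceptability *are* overstated. The documents do not show that: they give no dropout rate and no relation between dropout and outcome. *May be overstated* is as far as the evidence goes. If non-completers do not change, the completer mean is 1.11 to 1.5 times the all-starter mean for retention from 90% down to 67%. It is not inflated if nobody is lost, or if loss is unrelated to benefit. The 67% figure and the 10 abstainers are illustrations, not forecasts. The clustering result rests entirely on an assumed ICC and supports a sensitivity analysis at most, since a group effect is poorly estimated from 4 to 6 groups.

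**What to change.** 1. For vaping and questionnaire outcomes, include every vaper who starts MBSR (attends at least one session), with or without scan 2. Fit a mixed model over baseline and the follow-up visits. Put TLFB on a common scale, because Table 1 uses 28 days at Visit 1 and 7 days at Visits 12-15. State the missing-at-random assumption; the model cannot repair loss that depends on unobserved vaping.
2. Report abstinence with all starters as the denominator and missing counted as vaping, at least as a sensitivity analysis.
3. Call the two-scan imaging set a completer set, and compare its baseline with that of the remaining vapers.
4. Compute retention on all MBSR starters, define end of treatment, and report the already planned 50/75/100% attendance table beside the acceptability verdict.
5. Reconcile *completed* in Sections 4.4 and 9.3, and TLFB timing in Table 1 and Sections 9.4.3 and 9.4.5. State whether outcomes are collected after discharge under Section 7.1.

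Group clustering can be added as a sensitivity analysis.

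Cost: items 1 to 4 need wording in Section 9 and no new data. Because Section 9 is part of the protocol, the change goes through IRB review as an amendment, as would any change to what is collected after discharge. The downside is less favourable and somewhat wider estimates.

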9.4 Statistical Analyses

9.4.1 General Approach

Abbreviated Title: Mindfulness and Teen Vaping

Version Date: 07/21/2025

NIH IRB#: IRB001855

Quantitative analysis: For quantitative analysis of behavioral variables assessed at multiple time points, changes in scores across time will be presented descriptively (means, SDs) and analytically. Behavioral data encompasses scores on questionnaires assessing substance use variables, psychological functioning, and mindfulness processes. Paired t-tests will be used to examine pre- to post-treatment changes in continuous measures, and chi-squares will be used to test for pre- to post-treatment changes in categorical variables. Regression will be used to assess continuous relationships between scores on behavioral performance measures, self-report questionnaires, neuroimaging data (both pre-treatment and change from pre- to post-treatment), and outcome data.

fMRI data: resting time courses averaged from seeds of hippocampal subregions will be extracted and correlated with time courses from all other voxels in the brain on an individual level. Individual maps will be combined to obtain group level maps of connectivity from hippocampal subregions which will be compared between groups at baseline and within group pre- vs post-MBSR with t-tests.

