| | 
 - Engagement with MBSR training and post-training Craving-to-Quit app and change scores for other behavioral measure (e.g. vaping, emotion regulation). - rsFC from seeds such as dorsal anterior cingulate. |
| Study Population: | 40 nicotine vaping adolescents (13-18 years old) who vape 4-7 days per week, and 40 age, sex, race/ethnicity, SES matched typically developing (TD) adolescents with no nicotine vaping/tobacco smoking history. Participants will be recruited via online advertising, word of mouth, and from our vaping survey study. Recruitment will target the greater Baltimore area. To improve generalizability of our results, we will include youth who vape and who also smoke cigarettes (dual users) or co-use cannabis (co-MJ users) as well as those with stable psychiatric comorbidities. We will measure, control for, and exploratorily examine differences in these behaviors and groups in our analyses. |
| Phase or Stage: | This is a natural history study (comparison of teens who do and do not vape) and an open-label pilot study (comparison of teens who vape before and after MBSR training). |
| Description of Sites/Facilities Enrolling Participants: | The Biomedical Research Center of NIDA-IRP in Baltimore, MD, is the single site used for this study. |
| Description of Study Intervention: | The study intervention is a 9-week MBSR intervention once per week in-person or remotely (via an NIH approved remote platform used in compliance with policy, including HRPP Policy 303). The MBSR will be delivered to groups of 8-12 participants. Only the vaping adolescents will receive MBSR training. |
| Study Duration: | The study duration is approximately 24 months. |
| Participant Duration: | The participant duration is approximately 5.5-7 months, including baseline assessment and MRI scan 1, the 9-week MBSR intervention, and post-intervention assessment and MRI scan 2. There will also be a monthly follow-up for three months after the last MRI scan. Non-vaping participants will only complete baseline assessments and scan 1, which should take a week or less. |

Abbreviated Title: Mindfulness and Teen Vaping
Version Date: 07/21/2025
NIH IRB#: IRB001855

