5 STUDY POPULATION

5.1 Inclusion Criteria

In order to be eligible to participate in this study, an individual must meet all of the following criteria:

Non-Vaping group:

1. For adolescents aged 17 and under, parental/guardian informed consent to participate in the study
2. English language fluency
3. Males and females; Age 13-18 enrolled in grades 9-12, or the summer after graduation.
4. No MRI contraindications
5. No evidence of current psychosis, mania, or significant suicidality
6. If on medication for depression, anxiety or ADHD, dose has been stable for 3 months
7. No DSM-5 diagnosis of moderate or severe SUD related to a psychoactive substance, including tobacco, in the past year
8. Access to necessary resources for participating in a technology-based intervention, which includes smartphone ownership for this study
9. No use of nicotine more than 5 times in their life, and none at all in the last 30 days prior to enrollment.

Vaping group:

1. For adolescents aged 17 and under, parental/guardian informed consent to participate in the study
2. English language fluency
3. Males and females; Age 13-18 enrolled in grades 9-12, or the summer after graduation.
4. No MRI contraindications
5. No evidence of current psychosis, mania, or significant suicidality
6. If on medication for depression, anxiety or ADHD, dose has been stable for 3 months
7. No DSM-5 diagnosis of moderate or severe SUD related to another psychoactive substance (other than tobacco) in the past year
8. Vape a nicotine containing product at least 10 days in the past 30 days
9. Access to necessary resources for participating in a technology-based intervention, which includes smartphone ownership for this study

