9.4.2 Analysis of the Primary Endpoints

Behavioral data analysis: Group differences (Vaping vs. TD) will be evaluated via chi-squares, independent t-tests (Primary Endpoint 1). In addition to EOT nicotine abstinence, Δ scores will be calculated for each behavioral measure (e.g. vaping frequency, emotion regulation) and will be used for within-subject analyses to characterize MBSR-related behavioral change (Primary Endpoint 2).

rsFC fMRI data analysis: Seed-based ROI whole-brain rsFC analyses between *a priori* defined hippocampal seed regions and large-scale brain networks (focusing on DMN, ECN, SN). Whole-brain regression analyses will be conducted for each seed on each individual's preprocessed data resulting in a Fisher-transformed z-value in each brain voxel (**DV**). Seed regions: Right- and left-whole and sub-region hippocampal ROI seeds such as those defined via probabilistic voxel maps created by Chase *et al.*⁹⁹ will be used for rsFC analyses. Target network identification: Hypothesis-driven seed-based analyses will be constrained to voxels within each of three functionally generated masks of large-scale brain networks (DMN, ECN, SN) identified via group independent component analysis⁶ or taken from a published atlas.

s-rsFC Analysis: Independent and Paired t tests will examine group (Vaping vs. TD) (Primary Endpoint 1) and session (Pre/Post-MBSR) (Primary Endpoint 2) effects in s-rsFC strength between each hippocampal seed and voxels within each of the 3 network masks (e.g., seed-ECN voxels).

d-rsFC Analysis: d-rsFC will be estimated using a sliding window method^{21,22} creating windowed correlation matrices, to which a k-means clustering algorithm will be applied to identify states.⁶ Independent and Paired t-tests will examine group (Vaping vs. TD) (Primary Endpoint 1) and session (Pre vs. Post-MBSR) (Primary Endpoint 2) differences in d-rsFC DVs: state occupancy and transitions.

Correlational analyses: To test relationships between MBSR-related Δ rsFC and Δ vaping behaviors and other behavioral outcomes, we will use regression analyses.

Post-hoc analyses: Post-hoc ROI seed-based whole-brain connectivity analyses will test if the regions showing mindfulness-related Δ rsFC are distinct from or overlap with regions modulated by nicotine exposure (from Primary Endpoint 1).

Abbreviated Title: Mindfulness and Teen Vaping

Version Date: 07/21/2025

NIH IRB#: IRB001855

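### Section 9.4.1 names no paired test for pre-to-post change in categorical variables; an ordinary chi-square ignores the pairing or tests association instead of change

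*Combined protocol and SAP*

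**What the plan says.** Section 9.4.1 (General Approach) gives two rules for behavioural variables measured more than once. For continuous ones: "Paired t-tests will be used to examine pre- to post-treatment changes in continuous measures". For categorical ones: "chi-squares will be used to test for pre- to post-treatment changes in categorical variables". No McNemar, marginal-homogeneity or other paired categorical method is named in any section.

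Section 9.4.2 uses the same term for two separate groups: "Group differences (Vaping vs. TD) will be evaluated via chi-squares, independent t-tests (Primary Endpoint 1".

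Only vapers are measured twice; non-vapers complete baseline and one scan. Section 4.1 enrols up to 60 vapers "to obtain complete data on N=40 tobacco vaping youth 13-18 years old", so about 40 pairs are expected.

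Abstinence is mentioned once as an outcome, in Section 9.4.2: "In addition to EOT nicotine abstinence, Δ scores will be calculated for each behavioral measure". It has no look-back window, no test and no summary measure. Section 9.4.5 adds only that self-reported abstinence after MBSR will be verified by cotinine and CO.

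**The concern.** Pre and post values from one person are not independent. Two ordinary chi-square tests could be run under the Section 9.4.1 wording, and neither tests change properly.

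- **Time-by-category table.** The two measurements are stacked as if they came from different people. The test compares the right proportions with the wrong variance.
- **Pre-by-post table.** Each person is counted once, but the hypothesis is that the post value is unrelated to the pre value. Stable behaviour produces a small p-value even if nobody changes on balance.

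The first can hide a real change. The second can be misread as evidence of change. With about 40 pairs, in a pilot meant to inform later controlled trials, either would mislead on any categorical behavioural or substance-use variable compared pre to post.

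**Working it through.** **Inputs.** From the documents: about 40 pairs (Section 4.1) and the eligibility rule (Section 5.1). The plan gives no rate, effect, correlation or power for any categorical outcome, so there is no figure of its own to reproduce. Assumed here: two-sided 5% level, and the rates and within-person correlations φ shown.

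**Notation.** Of N = 40 people, a are yes/yes, b yes/no, c no/yes and d no/no (pre/post). Let x1 = a+b, x2 = a+c and s = x1+x2. No change means that b and c have equal expectation.

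**1. Time-by-category table.** Pearson's statistic reduces to 2N(b−c)² / [s(2N−s)]. McNemar's is (b−c)² / (b+c). The numerators agree; only the variance differs.

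Example: 30/40 before and 22/40 after, with b = 9 and c = 1.
- Pearson: 80 × 64 / (52 × 28) = 3.516, p = 0.061 (0.101 with continuity correction).
- Exact McNemar: 2 × (1 + 10) / 2^10 = 0.021.

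With equal rates, the true variance of the difference is (1−φ) times the variance Pearson assumes. Exact enumeration of all tables at N = 40, rate 60% at both times, gives:

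| φ | Type I error, stacked Pearson |
|---|---|
| 0 | 5.2% |
| 0.3 | 2.1% |
| 0.5 | 0.6% |
| 0.7 | 0.06% |

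Power for an assumed fall from 50% to 30%:

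| φ | Stacked Pearson | Exact McNemar | Mid-p McNemar |
|---|---|---|---|
| 0 | 45.8% | 35.4% | 42.4% |
| 0.3 | 44.8% | 47.8% | 56.8% |
| 0.5 | 43.5% | 62.7% | 72.3% |

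The loss therefore depends on positive correlation. At zero there is none. At φ = −0.2 (rate 50%) the stacked test errs the other way, with type I error 8.2%.

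**2. Pre-by-post table.** Pearson's statistic here is N times the squared sample correlation. At φ = 0.5 that is about 40 × 0.25 = 10, far above the 3.84 critical value, whether or not anything changed. Enumeration at 50% before and after gives 90.7% rejection. With a real fall from 50% to 30% and φ = 0, it rejects only 5.3% of the time.

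Single table: a = 25, b = 5, c = 5, d = 5, so no net change. Pearson is 40 × (125−25)² / (30 × 10 × 30 × 10) = 4.44, p = 0.035; McNemar gives p = 1. One expected count is only 2.5, and the p-value becomes 0.092 with Yates' correction or 0.085 with Fisher's test. The enumerated rejection rate is the firmer evidence.

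**3. Abstinence at baseline.** The rule is "Vape a nicotine containing product at least 10 days in the past 30 days". Assume the look-back windows end on the same day.
- 28-day window: at most 2 of the 10 days can fall outside it, so at least 8 fall inside. Baseline abstinence is zero.
- 7-day window: all 10 days can fall in the earlier 23, so at least 0 fall inside. Baseline abstinence is not ruled out.

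The synopsis describes "40 nicotine vaping adolescents (13-18 years old) who vape 4-7 days per week", which would rule it out. The assessment table in Section 1.3 sets the TLFB at 28 days at Visit 1 and 7 days at Visits 12–15. Section 9.4.5 says 28 days at baseline and at the post-MBSR MRI visit.

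If baseline is 0/40, the pre-by-post chi-square is undefined (empty row), and pairing adds nothing: with 4 abstinent afterwards, stacked Pearson gives p = 0.040 and uncorrected McNemar 0.046. Both test against a zero fixed in advance. The informative summary is the proportion: 4/40 = 10% (exact 95% interval 2.8% to 23.7%), or 6/40 = 15% (5.7% to 29.8%).

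**The case against.** **Loose naming.** McNemar's test is a chi-square test, so the authors may have meant it. That is possible. But t-tests are split into paired and independent, while one bare term covers both categorical settings; an analyst following the text would run Pearson. Even on the kind reading, the paired test is unspecified and the remedy is the same.

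**Little depends on it.** This stands. Section 9.1 assesses preliminary efficacy in reducing vaping with t-tests, Section 9.4.2 does the same for imaging, and the feasibility criteria in Section 9.4.3 are proportions against 75%. The listed efficacy outcomes are mainly counts and scale scores.

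**Stronger readings that the documents do not support.**
- A reader might infer that p-values for cotinine or drug-test status will be wrong. No section plans a pre-to-post test of either as a category. Section 9.4.1 describes behavioural data as questionnaire scores, and the outcome for which cotinine is listed is change in vaping frequency.
- A reader might infer that every vaper is non-abstinent at baseline by eligibility. That holds for a 28- or 30-day window, not for 7 days, and no window is defined.
- A reader might infer that the plan tests abstinence against baseline by chi-square. Section 9.4.2 lists it apart from the change scores and assigns no test; only the general rule could reach it.
- A reader might expect the stacked test to produce false benefits. Under positive correlation it does the opposite.

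**Conclusion.** The point holds in limited form. As written, Section 9.4.1 leads to a test that does not suit repeated measurements on the same people, and nothing elsewhere corrects it. The size depends on assumptions. With positive within-person correlation, which is plausible for substance use but not stated, the stacked test runs well below its nominal 5% and, at correlation 0.5, gives up about 19 power points against exact McNemar (62.7 − 43.5) in the 50% to 30% case. The cross-table version answers a different question at any rate or correlation. The finding covers categorical behavioural or substance-use variables compared pre to post; it does not touch the imaging endpoints or change in vaping frequency. It should be corrected before analysis, but it does not threaten the main results.

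**What to change.** In Section 9.4.1, replace chi-squares for pre-to-post change with McNemar's test (exact or mid-p) for binary variables and a marginal-homogeneity test for variables with more than two categories. Report the paired difference in proportions with a confidence interval. Keep chi-square for vaping versus TD.

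In Section 9.4.2, report end-of-treatment abstinence as a proportion with an exact 95% interval and no test against baseline; if a test is wanted, name a benchmark rate in advance. State the abstinence window. Reconcile the TLFB windows in Sections 1.3 and 9.4.5, and the vaping-frequency wording in Sections 1.1 and 5.1.

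Cost: one sentence in Section 9.4.1, one or two in Section 9.4.2, and the reconciling edits. Sample size is unaffected. Data collection changes only if the TLFB reconciliation alters a visit's window.
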